### 7.2.2 Special Assays or Procedures

The following PK parameters will be analyzed at [name] lab at the University of Iowa.

- Maximum plasma concentration ( $C_{max}$ )
- Time to  $C_{max}$  ( $T_{max}$ )
- Elimination rate constant ( $\lambda_z$ )
- Elimination half-life ( $t_{1/2}$ )
- Area under the curve to the final sample ( $AUC_{0-t}$ )
- Area under the curve to infinity ( $AUC_{\infty}$ )
- Oral clearance (CL/F)
- Oral volume of distribution (Vz/F)

Blood samples for PK analysis will be collected in tubes containing sodium heparin as the anticoagulant at baseline (prior to product administration), at 1, 2, 4, 6, 8, 10, 12, 24 hrs, and Days 2, 3, 4, 6, 8 and 15 days after dosing. The blood samples (10 mL) will be placed on ice after draw, and centrifuged within 1 hour at 4-8°C at approximately 3000 rpm for 15 min. The plasma will then be collected and stored frozen at -80°C until analyzed. Urine for oxfendazole, metabolites, and creatinine will be collected. Urine for PK analysis will be collected at baseline (prior to product administration) and for the first 24 hours after product administration with specific collections times of urine for oxfendazole, 0-4, 4-8, 8-12, 12-24. A urine creatinine value will be tested on the 12-24 hours sample and used to calculate creatinine clearance. Spot urine samples will be collected at 24 (+ 8 hrs) and on Day 3 after dosing; 10 mL will be saved, aliquoted and stored at -80°C until analyzed. After the study of each cohort is completed, the collected plasma and urine samples will be shipped to the analytical lab. Validated methods will be used to assay the oxfendazole concentration in each sample.

### **7.2.3 Specimen Preparation, Handling, and Shipping**

Instructions for specimen preparation, handling, storage, and shipping are included in the MOP.

## 8 ASSESSMENT OF SAFETY

### 8.1 Specification of Safety Parameters

Safety outcome measures are defined in Section 3.2 and include the rate of SAEs and non-serious severe AEs.

### 8.2 Methods and Timing for Assessing, Recording, and Analyzing Safety Parameters

#### 8.2.1 Adverse Events

**Adverse Event (AE):** International Conference on Harmonisation (ICH) E6 defines an AE as any untoward medical occurrence in a patient or clinical investigation subject administered a pharmaceutical product regardless of its causal relationship to the study treatment. An AE can therefore be any unfavorable and unintended sign (including an abnormal laboratory finding), symptom, or disease temporally associated with the use of a medicinal (investigational) product. The occurrence of an AE may come to the attention of study personnel during study visits and interviews of a study recipient presenting for medical care, or upon review by a study monitor.

All AEs, including solicited systemic (subjective and quantitative) reactions, not meeting the protocol-defined criteria for SAEs will be captured on the appropriate data collection form and electronic case report form (eCRF). Information to be collected for unsolicited AEs includes event description, date of onset, licensed study physician's assessment of severity and relationship to study product and alternate etiology (if not related to study product) (assessed only by those with the training and authority to make a diagnosis and listed on the Form FDA 1572 as the site principal investigator or sub-investigator), date of resolution of the event, seriousness and outcome. All AEs occurring while on study will be documented appropriately regardless of relationship. All AEs will be followed to resolution.

Any medical condition that is present at the time that the subject is screened will be considered as baseline and not reported as an AE. However, if the severity of any pre-existing medical condition increases at any time during the study, it will be recorded as an AE.

All AEs must be graded for severity and assessed for relationship to study product (see definitions below). Adverse events characterized as intermittent require documentation of onset and duration of each episode. The start and stop date of each reported AE will be recorded on the appropriate data collection form and eCRF.

FDA defines an AE as any untoward medical occurrence associated with the use of a drug in humans, whether or not considered drug related.

**Severity of Event:** All AEs will be assessed by a licensed study physician listed on the Form FDA 1572 as the site principal investigator or appropriate sub-investigator using a protocol-defined grading system (see Section 9.2.2). For events not included in the protocol-defined grading system, the following guidelines will be used to quantify severity:

- Mild (Grade 1): Events require minimal or no treatment and do not interfere with the subject's daily activities.
- Moderate (Grade 2): Events result in a low level of inconvenience or concern with the therapeutic measures. Moderate events may cause some interference with functioning and daily activities.
- Severe (Grade 3): Events interrupt the subject's usual daily activities and may require systemic drug therapy or other treatment. Severe events are usually incapacitating.

The severity of systemic and clinical laboratory adverse events will be assessed according to toxicity grading scales taken directly or adapted from the DMID Guidance for Toxicity Grading Scale for Healthy Adult and Adolescent Volunteers. ECG abnormalities will be assessed as per Appendix C.

**Relationship to Study Product:** The study clinician's assessment of an AE's relationship to study product is part of the documentation process, but it is not a factor in determining what is or is not reported in the study. If there is any doubt as to whether a clinical observation is an AE, the event should be reported. The relationship to study product must be assessed for all AEs using the terms: related or not related. In a clinical trial, the study product must always be suspect. To help assess, the following guidelines are used:

- Related – There is a reasonable possibility that the study product caused the adverse event. Reasonable possibility means that there is evidence to suggest a causal relationship between the study product and the adverse event.
- Not Related – There is not a reasonable possibility that the administration of the study product caused the event.

## 8.2.2 Adverse Events

Subjects will be queried at each visit as to whether they have experienced any new symptoms or adverse events. Common events that may be encountered are listed below. Vital signs including temperature, pulse and blood pressure will be recorded at each visit. Please refer to the toxicity table in Appendix B for grading of adverse events.

## 8.2.3 Serious Adverse Events

**Serious Adverse Event (SAE):**

An adverse event or suspected adverse reaction is considered “serious” if, in the view of either the investigator or sponsor, it results in any of the following outcomes:

- Death,
- a life-threatening adverse event\*,
- inpatient hospitalization or prolongation of existing hospitalization,
- a persistent or significant incapacity or substantial disruption of the ability to conduct normal life functions, or,
- a congenital anomaly/birth defect.
- Important medical events that may not result in death, be life-threatening, or require hospitalizations may be considered serious when, based upon appropriate medical judgment they may jeopardize the subject and may require medical or surgical intervention to prevent one of the outcomes listed in this definition. Examples of such medical events include allergic bronchospasm requiring intensive treatment in an emergency room or at home, blood dyscrasias or convulsions that do not result in inpatient hospitalization, or the development of drug dependency or drug abuse.

\* Life-threatening adverse event. An adverse event is considered “life-threatening” if, in the view of either the investigator or sponsor, its occurrence places the subject at immediate risk of death. It does not include an adverse event, had it occurred in a more severe form, might have caused death.

All SAEs will be:

- Assessed for severity and relationship to study product and alternate etiology (if not related to study product) by a licensed study physician listed on the Form FDA 1572 as the site principal investigator or sub-investigator.
- Recorded on the appropriate SAE form and eCRF.
- Followed through resolution or stabilization by a study physician licensed to make medical diagnoses and listed on the Form FDA 1572 as the site principal investigator or sub-investigator.
- Reviewed and evaluated by an Independent Safety Monitor (ISM), the SMC (periodic review unless related), DMID personnel including the medical monitor, and the IRB.

#### **8.2.4 Procedures to be Followed in the Event of Abnormal Laboratory Test Values or Abnormal Clinical Findings**

The site principal investigator or appropriate sub-investigator is responsible for reporting all AE/SAEs that are observed or reported during the study, regardless of the relationship to study product. AE/SAEs, abnormal clinical laboratory test values, or abnormal clinical findings will be documented, reported, and followed appropriately.

## 8.3 Reporting Procedures

### Reporting of Adverse Events:

AEs will be documented from the time of receipt of study drug on Day 1 (Visit 02) through approximately 14 days after receipt of study product.

SAEs will be documented from the time of receipt of study drug on Day 1 (Visit 02) through approximately 14 days after receipt of study product.

#### 8.3.1 Serious Adverse Events

Any AE that meets a protocol-defined serious criterion must be submitted immediately (within 24 hours of site awareness) on an SAE form to the DMID Pharmacovigilance Group, at the following address:

**DMID Pharmacovigilance Group  
Clinical Research Operations and Management Support (CROMS)  
[name] [name] 650  
Bethesda, MD 20814, USA**

**SAE Hot Line: [name] (US) or [name] (outside US)  
SAE FAX [contact] (US) or [name] (outside US)  
SAE Email Address: [[contact]](mailto:[contact])**

Other supporting documentation of the event may be requested by the DMID Pharmacovigilance Group and should be provided as soon as possible.

The DMID medical monitor and clinical protocol manager will be notified of the SAE by the DMID Pharmacovigilance Group. The DMID medical monitor will review and assess the SAE for regulatory reporting and potential impact on study subject safety and protocol conduct.

At any time after completion of the study, if the investigator becomes aware of an SAE that is suspected to be related to study product, the investigator will report the event to the DMID Pharmacovigilance Group.

#### 8.3.2 Regulatory Reporting for Studies Conducted Under DMID-Sponsored IND

Following notification from the investigator, DMID, the IND sponsor, will report any suspected adverse reaction that is both serious and unexpected. DMID will report an adverse event as a suspected adverse reaction only if there is evidence to suggest a causal relationship between the drug and the adverse event. DMID will notify FDA and all participating investigators (i.e., all investigators to whom the sponsor is providing drug under its INDs or under any investigator's IND) in an IND safety report of potential serious risks from clinical trials or any other source, as soon as possible, but in no case later than 15 calendar days after the sponsor determines that

the information qualifies for reporting as specified in 21 CFR Part 312.32. DMID will also notify FDA of any unexpected fatal or life-threatening suspected adverse reaction as soon as possible but in no case later than 7 calendar days after the sponsor's initial receipt of the information. Relevant follow-up information to an IND safety report will be submitted as soon as the information is available. Upon request from FDA, DMID will submit to FDA any additional data or information that the agency deems necessary, as soon as possible, but in no case later than 15 calendar days after receiving the request.

All serious events designated as "not related" to study product(s), will be reported to the FDA at least annually in a summary format.

### **8.3.3 Reporting of Pregnancy**

Not applicable. Females of childbearing potential are excluded from enrollment in the study.

## **8.4 Type and Duration of Follow-up of Subjects after Adverse Events**

AEs and SAEs will be followed from the time of the first receipt of study drug Day 1 (Visit 02) through the last subject's study visit.

AEs and SAEs will be followed until resolution even if this extends beyond the study-reporting period. Resolution of an AE/SAE is defined as the return to pretreatment status or stabilization of the condition with the expectation that it will remain chronic.

If the site principal investigator or appropriate sub-investigator becomes aware of a sign or symptom and the site principal investigator or appropriate sub-investigator decides to bring the subject in for an evaluation to determine etiology, then the site principal investigator or appropriate sub-investigator, at their own discretion, can determine what further testing is appropriate.

Follow-up procedures, evaluations, and outcomes will be recorded on the appropriate data collection form.

## **8.5 Halting Rules**

Two sentinel subjects (1 study drug and 1 placebo) will be dosed and monitored 48 hours for adverse events prior to enrolling the remaining subjects in each cohort. If no drug-related SAE or grade 3 study drug related laboratory AE occurs in the sentinel subjects after 48 hours of observation, the remainder of the cohort may proceed with dosing.

An SRC composed of the Protocol Principal Investigator and Independent Safety Monitor will review blinded safety data for each completed cohort. Each new cohort will be dosed only after the 2-week safety data for the preceding group have been reviewed for the following events:

- The SRC will evaluate the safety data from each dose group and will allow continuation if there are no product related grade 3 AEs or if there are fewer than two product related grade 2 AEs identified.

Enrollment, dosing and study procedures will be halted for SMC review/recommendation if any of the following are reported:

- Any death occurring after administration of study drug through the subject's last study visit that was not the result of trauma or accident, regardless of relatedness to study product.
- Any subject experiences laryngospasm, bronchospasm, or anaphylaxis within 24 hours after administration of study product.
- Any subject experiences a study drug-related Stevens Johnson Syndrome.
- Two or more subjects experience generalized urticaria within 72 hours after administration of study product.
- Any subject experiences a study drug-related SAE from the time of receipt of study drug through the subject's last study visit.
- Any subject develops new EKG changes that are deemed significant by a reviewing cardiologist.
- Any subject develops grade 3 laboratory abnormalities deemed related to the study drug.
- The SRC members are not unanimous in their agreement to proceed to the next dosing group or cannot assess or do not unanimously agree on the relatedness of the adverse event to the study product.

If any of the halting rules are met following any subject receipt of study drug, the study will not continue with the remaining enrollments without a review by and recommendation from the SMC to proceed.

DMID retains the authority to suspend additional enrollment and study interventions/administration of study product during the entire study, as applicable.

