This Phase I study is a randomized, double-blind, placebo-controlled evaluation of the safety and pharmacokinetics of escalating single oral doses of oxfendazole (0.5 to 60 mg/kg) in healthy volunteers. Up to 70 volunteers will participate in this study. The dose will be increased approximately three-fold (one-half log) at each increment, and each cohort will comprise 10 volunteers (8 subjects will receive study drug and 2 will receive placebo). Two sentinel subjects (1 drug/1 placebo) in each cohort will be monitored for 48 hours after receiving the study drug prior to completing enrollment in the cohort. Subjects will be monitored for two weeks after dosing, including monitoring the pharmacokinetics and metabolism of oxfendazole in blood and urine. Each new cohort will be dosed only after the two week safety data for the preceding group have been reviewed. If a clinically significant AE is observed, and if this event is drug-related the safety monitoring committee will be convened to determine whether the study should continue.

**Estimated Time to  
Complete Enrollment:**

17 months

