**Schematic of Study Design:**

Note: Two sentinel subjects will receive the study product (1 drug/1 placebo) in each group and be monitored 48 hours for adverse events prior to completing enrollment of the remaining 8 subjects in the group. Adverse events assessed as related to the study product and as defined in the Halting Rules may result in suspension of the study.

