## 4 STUDY DESIGN

This Phase I study is a randomized, double-blind, placebo-controlled evaluation of the safety and PK of escalating single oral doses of oxfendazole (0.5, 1, 3, 7.5, 15, 30, 60 mg/kg) in healthy volunteers. The dose will be increased approximately three-fold (one-half log) at each increment, and each cohort will comprise 10 volunteers (8 drug, 2 placebo). Subjects will be monitored for 2 weeks after dosing, including monitoring the PK and metabolism of oxfendazole in blood and urine.

Two sentinel subjects (one randomized to receive study drug and the other to receive placebo) will be dosed and monitored 48 hours for adverse events prior to enrolling the remaining subjects in each cohort. If no drug-related serious adverse event or laboratory grade 3 study drug related events are observed within the 48 hour period, the remainder of the cohort will proceed with dosing. Each new cohort will be dosed only after the 2-week safety data for the preceding group have been analyzed. A Safety Review Committee (SRC) composed of the Protocol Principal Investigator and Independent Safety Monitor will review blinded safety data for the completed cohort. If a clinically significant AE is observed that is possibly drug related, the SRC will determine if an ad hoc SMC meeting should be called. Up to 70 volunteers (56 drug, 14 placebo) will complete the study. The Safety Monitoring Committee (SMC) will review the safety data either when or if the final dose is reached.

For the Phase I study, between 10 and 70 subjects (8:2 drug: placebo in each cohort receiving increasing doses) will be enrolled. This number should be small enough to perform the study safely and efficiently, yet large enough for an estimation of the PK, metabolism, and the identification of any common side effects of oxfendazole.

The study will be conducted on an outpatient basis at the University of Iowa. Screening for subject recruitment will continue throughout the study until the requisite number of volunteers is enrolled. Each subject will be evaluated over a 2 week period. Projected duration of subject participation will be 3-6 weeks of face to face visits, including the screening period. It is anticipated that it will take 18 months to finish the study.

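### The 48-hour sentinel gate does not by rule hold the other 7 drug subjects after a related, non-serious Grade 3 clinical AE that is not a named halting event

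*Protocol*

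**What the plan says.** **The gate.** Each cohort has 8 drug and 2 placebo subjects. One of each is dosed first and watched for 48 hours. Protocol Section 8.5 states the test as "If no drug-related SAE or grade 3 study drug related laboratory AE occurs in the sentinel subjects after 48 hours of observation". Its consequence is permissive: "sentinel subjects after 48 hours of observation, the remainder of the cohort may proceed with dosing". Section 4 has the same two triggers but a mandatory consequence: "laboratory grade 3 study drug related events are observed within the 48 hour period, the remainder of the cohort will proceed with dosing". SAP Section 3.1 repeats the Section 4 wording.

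**The halting rules.** The only study-level bullet in Section 8.5 that turns on severity grade is "Any subject develops grade 3 laboratory abnormalities deemed related to the study drug". The others cover non-accidental death, three airway or anaphylactic events within 24 hours, related Stevens Johnson Syndrome, generalized urticaria in two or more subjects, any related SAE, EKG changes a cardiologist considers significant, and SRC disagreement or inability to assess relatedness. The sentinel note under the Schematic of Study Design refers back to this list: "Adverse events assessed as related to the study product and as defined in the Halting Rules may result in suspension of the study".

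**The cohort-level rule.** The SRC (the principal investigator and the Independent Safety Monitor, ISM) "will allow continuation if there are no product related grade 3 AEs or if there are fewer than two product related grade 2 AEs". This has no laboratory restriction, but it applies to a completed cohort (Section 8.6.2).

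**Convening the Safety Monitoring Committee (SMC).** For a clinically significant AE, the Protocol Summary says "if this event is drug-related the safety monitoring committee will be convened to determine whether the study should continue". Section 4 says instead that "the SRC will determine if an ad hoc SMC meeting should be called".

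**The concern.** This is a first-in-human trial, and Section 2.3.1 expects gastrointestinal events and rare allergic reactions, both of which appear as clinical signs. The sentinel step exists to show such a signal in one drug-treated subject before seven more receive the same dose. As written, it reacts to a related Grade 3 laboratory value but not to a related Grade 3 clinical event of equal grade, unless that event is serious or on the named list.

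The clearest example is a single case of generalized urticaria. Appendix B grades it 3, but the halting rule needs two subjects. Headache or vomiting severe enough to stop daily activity is also Grade 3. Either could pass the gate if the investigator did not class it as serious. The plan would count such an event when deciding on the next dose, but no rule makes the site wait before finishing the current one. Sections 4 and 8.5 also differ on whether dosing then goes ahead or merely may go ahead.

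**Working it through.** **Step 1. Follow the uncovered case through the rules.** Take a drug sentinel with a Grade 3 clinical AE that is non-serious, agreed to be related and not a named event.

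| Provision | Applies? | Holds the other 7? |
|---|---|---|
| Sentinel gate (Protocol 4, 8.5; SAP 3.1) | No: neither an SAE nor a laboratory event | No |
| Grade 3 halting bullet (8.5) | No: laboratory only | No |
| SRC disagreement or inability to assess (8.5) | No: relatedness is agreed | No |
| SRC criterion on Grade 3 AEs (8.5, 8.6.2) | Yes, after the cohort is complete | Too late |
| SMC convened (Protocol Summary) | If judged clinically significant; no grade given | No hold stated |
| Ad hoc SMC meeting (4, 8.6.3), ISM review (8.6.1), sponsor suspension or termination (8.5, 4.3.5) | Possibly | Discretionary |

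**Step 2. Check the formula against the plan.** The gate has no figure of its own. Table 4 in Section 10.2 uses P(at least one event in n) = 1 − (1 − p)^n. For n = 8 and p = 0.18 this gives 1 − 0.82^8 = 0.796, against the stated 80%.

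**Step 3. Inputs.** Drug subjects left after the sentinel: 8 − 1 = 7 (Section 4). Event rate p: not in the documents. I assume 1%, 5% and 10%, the same at every dose and independent between subjects.

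**Step 4. Size of the gap.**

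| Quantity | p = 1% | p = 5% | p = 10% |
|---|---|---|---|
| Further case among 7, given a sentinel event: 1 − (1 − p)^7 | 0.068 | 0.302 | 0.522 |
| Expected further cases: 7p | 0.07 | 0.35 | 0.70 |
| Joint chance per cohort: p × [1 − (1 − p)^7] | 0.0007 | 0.0151 | 0.0522 |

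These are cases that a review could act on, not cases certain to be averted.

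**Step 5. Added pauses from widening the gate.** Per cohort the chance is p, because one drug subject is a sentinel. The trial-level chance depends on what follows an event.

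- All 7 cohorts run regardless: 1 − (1 − p)^7 = 7%, 30%, 52%.
- Escalation stops after any such event among a cohort's 8 drug subjects: with q = (1 − p)^8, the chance is p × (1 − q^7)/(1 − q).
  - 1%: q = 0.923, factor 5.57, result 5.6%.
  - 5%: q = 0.663, factor 2.80, result 14%.
  - 10%: q = 0.430, factor 1.75, result 18%.
- All cohorts run, and placebo-sentinel events are attributed to drug at the same rate: 1 − (1 − p)^14 = 13%, 51%, 77%.

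**Step 6. The same stopping rule applied to the joint chance.** Multiplying the Step 4 joint chance by the factors in Step 5 gives 0.4%, 4.2% and 9.1% over the trial. Running all 7 cohorts regardless gives 0.5%, 10% and 31%.

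**The case against.** The strongest reply is that the laboratory focus is deliberate and the rest is covered elsewhere. Bone marrow and liver are the main target organs (Sections 2.1.1.4 and 2.3.1), and the gravest clinical hazards are named one by one in Section 8.5. Many incapacitating Grade 3 events would also meet the SAE definition in Section 8.2.3. With one drug and one placebo sentinel under blinding, relatedness may be unclear, and SRC inability to agree on it is itself a halting event. Section 8.5 only permits dosing to continue. The investigator or the ISM can ask for an SMC meeting (Section 8.6.3), and the sponsor can suspend or terminate.

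All of that stands, and it narrows the gap. It does not close it, because none of these provisions requires dosing to wait when a non-serious, unnamed Grade 3 clinical AE is agreed to be related. The Protocol Summary sentence comes nearest, but it sets no grade and no hold, and Section 4 leaves the meeting to the SRC.

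A reader might infer that the protocol compels dosing of the next 7 after any severe clinical reaction, or has no safeguard against it. The documents do not support that: Section 8.5 is permissive, and the routes above are real. A reader might also take the largest whole-trial figures (31% for the joint chance, 52% for an added pause) as the expected size. Those need a 10% rate at every dose from 0.5 to 60 mg/kg and all 7 cohorts run despite the SRC criterion. The documents support neither assumption.

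**Conclusion.** The point holds in limited form. The gap rests on the text alone: the gate omits one class of event that the plan itself counts against escalation, and 7 more drug subjects could be dosed before that count is made. Its numerical size cannot be fixed from the documents. The per-cohort figures (0.07%, 1.5% and 5.2% on assumed rates of 1%, 5% and 10%) are the most defensible illustration, because they need no assumption about whether later cohorts run. This is a worthwhile, cheap improvement to a first-in-human safety rule. It does not bear on the sample size or the analysis.

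**What to change.** In Protocol Sections 4 and 8.5 and SAP Section 3.1:

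- Make the gate condition the absence of a drug-related SAE and of a drug-related Grade 3 AE, whether clinical or laboratory.
- Use the permissive form (the rest of the cohort may proceed) in all three places.
- State that if the gate fails on a Grade 3 clinical AE, the rest of the cohort is held until the SRC has reviewed the event ad hoc and either cleared dosing or referred it to the SMC. Related SAEs and related Grade 3 laboratory events continue to go to the SMC under the existing halting rules.

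No separate urticaria clause is needed, since generalized urticaria is already Grade 3 in Appendix B. The study-level halting bullets should stay as they are. Widening the Grade 3 bullet to clinical events would trip it at least once over 56 drug subjects with probability 1 − 0.99^56 = 43% at a 1% rate and 1 − 0.95^56 = 94% at 5%, if all are dosed.

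The cost is wording only: AEs are already graded and assessed for relatedness (Section 8.2.1). The operational price is an added pause with probability 1%, 5% or 10% per drug sentinel at the assumed rates. Over the trial that is 5.6%, 14% or 18% if escalation stops after any such event, up to 7%, 30% or 52% if every cohort runs, and more if placebo-sentinel events are attributed to drug. Review by the two SRC members should keep each pause short.
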